5. STUDY DESIGN

5.1. Overall Design

This is a China-based multi-center, prospective, longitudinal, real-world study, taking a naturalistic approach, capturing real-world medical practice and patient outcomes using a non-interventional design. Patients with diagnosed CHB who newly initiate and continue TDF monotherapy or combination therapy will be consecutively recruited from general and specialized hospitals across China. Site/hospital selection will consider geographic and hospital type/tier representativeness, investigators' research interest, as well as feasibility such as electronic data collection approaches. For non-enrolled subjects, reasons of exclusion will be collected.

During the study, patients will seek and receive medical care as they do in regular clinical practice setting without investigational product tested. Specifically, patients' diagnosis, treatment, and monitoring will be left to their physicians' routine practice without study-

dictated visits and procedures. Minimal patient evaluations will be done by physicians, e.g. baseline patient demographics and clinical characteristics and patients' treatment adherence. Minimal lab tests in line with routine clinical practice (HBV DNA, serum creatinine, and serum phosphate) will be conducted in a central lab on the basis of the judgement of treating physicians and willingness of patients.

Other patient data will be collected using electronic approaches, mainly from lab test reports or medical records at the entry of this study and thereafter at 6-month intervals for 3 years. As this is a real-world study without mandatory scheduled visits, patients may not seek medical care and conduct assessments (e.g. lab tests) exactly at 6-month intervals. The 6-month interval is set to remind investigators to collect data regularly.

5.2. Number of Participants

Approximately 2000 eligible CHB patients will be recruited from general and specialized hospitals across China.

5.3. Participant and Study Completion

The recruited 2000 TDF-treated CHB patients will be followed up to 3 years as treatment group to evaluate the effectiveness of safety of TDF in real-world setting in China without study-specified intervention and procedure. All the recruited patients will seek and receive medical care as they do in regular clinical practice setting during the study follow-up and after the study completion with no study medicine provided.

5.4. Scientific Rationale for Study Design

Although evidence on TDF efficacy and safety has been accumulated in traditional clinical trials, there is a lack of real-world evidence on its effectiveness and safety, especially among Chinese CHB patients. CHB patients are a heterogeneous population, with a wide range of age, morbidities and comorbidities, such as renal impairment. However, many of these patients are usually excluded from traditional clinical trials. The importance of real-world evidence is increasingly acknowledged because real-world studies provide valuable information about the use of treatments in daily clinical practice, as they include patient populations usually under-represented in clinical trials and capture real-world practice and patient outcomes.

To explore the effectiveness and safety of TDF, this study will take a naturalistic approach using a non-interventional and prospective design, reflecting the real-world patient population and disease management. Evidence from this real-world study will be of great relevance and value to inform physicians, patients and payers to better understand the benefits and risks of TDF, guide physicians' practice on managing CHB patients, aid payers in decision-making on resource allocation, and ultimately provide more benefits to Chinese CHB patients.

5.5. Dose Justification

Not applicable for this study in which no study intervention will be administered.

6. STUDY POPULATION

TDF-naïve patients with confirmed diagnosis of CHB who newly initiate (Viread) monotherapy or combination therapy for the treatment of CHB will be invited to participate in this study. Those who have already started TDF treatment and meet all the inclusion and exclusion criteria will be also considered eligible. To minimize selection bias, investigators are encouraged to follow their routine clinical practice and consecutively recruit all eligible patients at their practice. More importantly, patients will only be approached for participation after his/her treatment choice has been naturally made between him/her and the physician/investigator (e.g. whether to get treatment or what anti-viral treatment). Willing participants (or their legal guardian) will be asked to voluntarily provide the informed consent to allow their past, current and follow-up medical information to be collected within the study period. For non-enrolled subjects, the reasons for exclusion will be collected whenever possible.

Hospitals and investigators will be selected mainly based on the representativeness of hospital tier, geographic, the research interest of a specific physician to this study, and the potential CHB patient flow. To better understand the real-world practice in Chinese hospitals, we performed a feasibility assessment among infectious disease physicians in 17 hospitals across the country, including 8 Tier 3 Grade A general hospitals, 6 Tier 3 Grade A infectious disease specialized hospitals, and 3 Tier 2 Grade A general hospitals. 11 out of 17 physicians showed interest in this study and the evidence on TDF's effectiveness and safety in real world setting. The majority of interviewed physicians stated that over 50 CHB patients could be recruited in their practice within 3 months.

6.1. Inclusion Criteria

Participants will be eligible to be included in this study only if all of the following criteria apply:

- 1. Male or female participants aged 12 years and above, at the time of signing the informed consent.
- 2. Participants who are diagnosed with CHB and meet the criterion of antiviral treatment for HBV infection judged by certified physicians.
- 3. Participants who newly initiate TDF ((only including brand TDF, Viread, and generic TDF, Beixin and Naxinde, which passed China generic quality consistency evaluation by Apr. 1 2018) monotherapy or combination therapy for the treatment of CHB by the judge of investigators at the study entry.
- 4. Participants who have already started TDF at the entry of study and will continue to be treated TDF (including brand TDF, Viread, and generic TDF, Beixin and Naxinde which passed China generic quality consistency evaluation by Apr. 01 2018) with essential medical information record and lab test reports available at the initiation of TDF treatment and follow-up visit.

Essential medical information record and lab test reports:

• *At the initiation of TDF treatment:*

- i. TDF treatment detail: TDF dose, brand name, start date;
- ii. Lab test (within +/-4 weeks of TDF treatment initiation): HBV DNA quantification (using high sensitive real-time PCR assays for HBV DNA quantification with lower limit of detection of 20IU/ml), ALT and/or AST, Serum creatinine and Serum phosphate, HBsAg/Anti-HBs and HBeAg/Anti-HBe
- iii. Medical information: CHB diagnosis and treatment history, co-morbidity, concomitant treatment
- The following visits under TDF treatment prior to entry of the study (At least once following visit record if TDF treatment >6 months):
 - i. Lab test: HBV DNA quantification (using high sensitive real-time PCR assays for HBV DNA quantification with lower limit of detection of 20IU/ml), Serum creatinine and Serum phosphate
 - ii. Medical information: co-morbidity, concomitant treatment, TDF treatment information

The proportion of patients who have already started TDF at the study entry will be monitored closely during study recruitment and will be kept less than 10% of the total study population.

- 5. Participants who are able to perform normal activities and seek regular medical care, e.g., willing to regularly perform lab test to monitor the treatment response.
- 6. Participants or their legal guardians who are capable of providing signed informed consent which includes compliance with the requirements and restrictions listed in the informed consent form (ICF) and in this protocol.

6.2. Exclusion Criteria

Participants will be excluded from the study if any of the following criteria apply:

- 1. Participants who have HIV/HCV co-infection.
- 2. Participants who initiate or continue antiviral treatment of generic TDF which did not pass China generic quality consistency evaluation by Apr. 01, 2018
- 3. Participants who initiate antiviral treatment of unauthorized TDF in China.
- 4. Participants with a prior history of receiving any TDF monotherapy or combination therapy without essential lab test report (e.g. HBV DNA level, eGFR, serum phosphate) and medical records available at the initiation of TDF treatment and thereafter follow-up.
- 5. Participants who participate in any concurrent clinical trials or within 3 months prior to the entry into this study.
- 6. Participants who are NOT able to upload their information electronically using the study-designed smartphone APP.
- 7. Inability to comply with study requirements as determined by the study Investigator.

6.3. Lifestyle Restriction

Not applicable for this study in which no study-specified intervention will be administered.

6.4. Screen Failure

When screening, relevant information will be collected as part of the participant's routine clinical management (e.g., blood count) and obtained before signing of ICF. The investigator will maintain a screening log to record details of all participants screened and to confirm eligibility or record reasons for study exclusion.

7. STUDY ASSESSMENTS AND PROCEDURES

Given the naturalistic nature of the study design, all participated patients will be diagnosed, treated, and monitored as in real clinical practice according to their physicians' judgement without additional interventions and procedures. Protocol-specified information relevant to CHB diagnosis and treatment will be collected from assessments generated from routine clinical care, including lab tests and medical records, complemented with investigators' evaluation at the entry of this study and thereafter at 6-month intervals for up to 3 years until the end of the study or until participant withdraws from this study. It is expected that diagnosis and treatment practice will vary across study hospitals and physicians.

Data will be collected using an innovative electronic approach, i.e. Smartphone App, with the intention to reduce the data collection burden on patients, investigators, and sites and also improve data collection efficiency and quality. The use of Smartphone App enables patients and investigators to upload lab tests and medical records and complete brief online evaluations (e.g. whether the patient remains on TDF? Any changes on TDF treatment?) via their smartphones.

There are no mandatory visits during the study period, however, according to the CHB clinical practice and CHB management guideline, CHB patients on anti-viral treatment should be monitored for at least every 6 months, e.g. HBV DNA, liver and renal function. Data collected and their timing are summarized in the SoA (See Section 2). The 6-month data collection interval is set to remind investigators to collect patient's data regularly. A minimal necessary medical evaluation in line with routine clinical practice following the guideline recommendation is required for all eligible patients at the entry of study for basic medical assessment on the basis of the judgement of treating physicians and willingness of patients. Other lab tests and procedures in the SoA will be judged by the treating physician and carried out by patients. Only available and identifiable assessments will be collected.

All the lab test and procedures in the SoA will be performed based on the judgement of investigators/treating physicians and patients' willingness as in real-world practice. To achieve consistent evaluation of the effectiveness and safety of TDF treatment, the minimal essential lab test requested by CHB management guideline, including HBV DNA, eGFR and serum phosphate, will be performed in central lab during patients'

routine clinical visits. Other lab tests and procedures will be performed in local hospitals where patients seek care. Results will be collected by the innovative electronic approach.

CONFIDENTIAL

Supplementary central lab operation information would be provided in the accompanying study procedure manual (SPM). The SPM will provide the site personnel with administrative and detailed information on how to minimize the impact of the introduction of central lab to routine practice.

7.1. Baseline Evaluation

Necessary and mandatory baseline evaluations must be completed and reviewed to confirm that potential participants meet all eligibility criteria (refer to Section 6). The investigator will maintain a screening log to record details of all participants screened and to confirm eligibility or record reasons for study exclusion, as applicable. Information collected as part of the participant's routine clinical management (e.g., blood count) and obtained before signing of ICF may be utilized for screening purposes provided the information met the protocol-specified criteria and was collected within the time frame defined in the SoA (Table 1).

The investigator will maintain a log to confirm eligibility or record reasons for study exclusion.

7.2. Baseline Data Collection

Baseline information collected (assessment values and date of assessment) includes:

- Socio-demographic information, e.g. age, sex, economic status, medical insurance coverage
- Health behaviour information, e.g. smoking status, alcohol consumption, health care seeking behaviour
- Physical examinations, e.g. weight, height
- Medical information, e.g. medical history, anti-Hep B diagnosis and treatment history, NUC drug resistance history, co-morbidity, concomitant treatment, decompensated cirrhosis/liver disease and related complications
- TDF treatment details, e.g. TDF dose, brand name, start date
- Initial tests when initiating TDF therapy, including
 - HBV serology
 - o HBV DNA
 - o Serum creatinine and eGFR [MDRD equation]
 - Serum phosphate
 - o Alanine transaminase (ALT) and aspartate transaminase (AST)
- Other tests and procedures collected if available
 - o AFP

- Hepatic ultrasound
- o Genotype
- o Bone mineral density
- o Liver biopsy
- o Transient elastography (fibrotouch or fibroscan)
- Hepatic ultrasound/ computed tomography (CT) /magnetic resonance imaging (MRI)
- Spontaneous AEs if available

To evaluate renal function, the estimated glomerular filtration rate (eGFR) will be calculated using the modification of Diet in Renal Disease (MDRD) equation:

Where the unit of creatinine is ml/min/1.73m². Baseline data will be collected using a specifically designed survey. For patients who initiate TDF treatment at the entry of the study, baseline information can be completed from investigator interviewing the patient.

For patients who have already been on TDF treatment at the study entry, their previous data related to initiation of TDF treatment and follow-up will be collected from (electronic) medical records as needed if available.

Three essential lab tests, HBV DNA, serum creatinine, and serum phosphate, will be performed in a central lab. Patients' other data will be collected using electronic approaches, mainly from lab test reports or medical records at baseline and follow-ups.

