7.3. Follow Up Data Collection

Study participants will be followed up for 3 years or until they withdraw from the study. Follow-up information will be collected at 6-month intervals:

- Regular tests
 - o HBV serology
 - o HBV DNA
 - o Serum creatinine and eGFR [MDRD equation]
 - Serum phosphate
 - Alanine transaminase (ALT) and aspartate transaminase (AST)
- Other tests and procedures
 - o AFP
 - o Hepatic ultrasound
 - Genotype
 - o Bone mineral density

- Liver biopsy
- o Transient elastography (fibrotouch or fibroscan)
- Hepatic ultrasound /computed tomography (CT) /magnetic resonance imaging (MRI)
- Updated CHB treatment details, e.g. any change to regimen or dosage and reason for change
- Comorbidity and concomitant medication review
- Spontaneous AEs if available
- For treatment adherence, it will be evaluated by the treating physician according to the patients' care seeking care, e.g. whether take the medication as prescribed, have you ever discontinued your medications and for how long?
- For participants who discontinue TDF prematurely, duration of treatment and reasons for TDF discontinuation will be recorded, e.g. SAEs, non-SAEs, and insufficient effectiveness.

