9.3.3. Secondary Analyses

Patients' renal functional change during TDF treatment period will be explored.

- The proportion of patients whose eGFR (MDRD equation) decline >20% from baseline at weeks of 48, 96 and up to week 144 will be summarized for the overall study analysis population and sub-group populations.
- Mean and 95% confidence intervals for the change from baseline in eGFR values will be calculated for the overall analysis population, as well as for the subpopulations of interests. A mixed effect model will be fitted to explore the impacts on the mean change from baseline in eGFR of fixed effects of age, gender, treatment-naïve or experienced, ADV or non-ADV, type of baseline comorbidities (Cirrhosis, Hypertension, diabetes mellitus (DM), non-overlapping), baseline eGFR values, baseline HBV-DNA counts, baseline HBeAg status, and other factors as appropriate, and random effects of subject ID.
- The percentage of change from baseline in eGFR will be estimated for the overall analysis population and by sub-populations at weeks 48, 96, and 144. Figures of mean eGFR values overall and the sub-populations of interests will be generated.
- The proportion of patients with confirmed a serum phosphate Grade 3 or 4 abnormality (<2.0 mg/dL) at weeks of 48, 98 and 144 will be summarized for the overall study analysis population and sub-group populations.
- The percentage of change from baseline in serum phosphate will be estimated for the overall analysis population and by sub-populations at weeks 48, 96, and 144. Figures of mean serum phosphate values overall and the sub-populations of interests will be generated.
- Mean and 95% confidence intervals for the change from baseline in serum phosphate values will be calculated for the overall analysis population, as well as for the sub-populations of interests. A mixed effect model will be fitted to explore the impacts on the mean change from baseline in serum phosphate of fixed effects of age, gender, treatment-naïve or experienced, ADV or non-ADV, type of baseline co-morbidities (Cirrhosis, Hypertension, DM, non-overlapping), baseline eGFR values, baseline HBV-DNA counts, baseline HBeAg status, baseline phosphorus and other factors as appropriate, and random effects of subject ID.

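### Enrolment opens at age 12, but every eGFR value and the >20% decline endpoint use MDRD, which has no growth term, so growth-related creatinine rises in adolescents count as renal decline

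*Protocol*

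**What the plan says.** Inclusion criterion 1 (Protocol 6.1) reads "Male or female participants aged 12 years and above, at the time of signing the informed consent". No adolescent stratum is defined.

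Section 7.2 fixes the equation: "the estimated glomerular filtration rate (eGFR) will be calculated using the modification of Diet in Renal Disease (MDRD) equation". Section 7.3 repeats it in the list of follow-up tests ("Serum creatinine and eGFR [MDRD equation"), and the Schedule of Activities names it in the creatinine row. No other eGFR equation appears.

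Section 9.3.3 puts the equation inside the endpoint: "The proportion of patients whose eGFR (MDRD equation) decline >20% from baseline at weeks of 48, 96 and up to week 144", for the overall population and for subgroups. It adds that "Mean and 95% confidence intervals for the change from baseline in eGFR values will be calculated for the overall analysis population", and specifies a mixed model for that change with "fixed effects of age, gender, treatment-naïve or experienced, ADV or non-ADV" and further covariates, none of which is height or growth.

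Height is listed as part of the physical examination in 7.2. The Schedule of Activities marks that examination at study entry only, and the follow-up list in 7.3 does not include it.

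Directly after the place where the formula should stand, 7.2 says "Where the unit of creatinine is ml/min/1.73m²".

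**The concern.** MDRD takes creatinine, age and sex. It cannot tell a creatinine rise caused by increasing muscle mass from one caused by falling filtration. In an adult followed for three years that distinction seldom matters. In a participant who enters at 12 and leaves at about 15 it does, because creatinine can rise with growth while true GFR stays constant.

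Three of the six secondary research questions in Table 2 rest on this value: decline above 20%, percentage change and absolute change in eGFR. The first is a raw proportion, so nothing adjusts it for age. In the mixed model, growth-related decline would load onto the age effect. The rationale in 3.2 says the study should address physicians' concern about the renal safety of TDF. An artefact in the youngest patients that looks like renal harm works against that purpose.

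**Working it through.** **The plan's own figure.** The protocol gives no expected rate for the eGFR endpoint and no expected number of adolescents. Its one sizing figure is the precision for CVR in 9.1.2: 1.96 × √(0.80 × 0.20 / 1300) = 0.0217, which agrees with the stated 2.2%. That figure is not in dispute. The 1,300 completers (2,000 less 35%) are used below.

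**Inputs.** From the protocol: minimum age 12; visits at weeks 48, 96 and 144 (week 144 = 144 × 7 / 365.25 = 2.76 years); threshold a decline above 20%. Assumed: the standard MDRD exponents, −1.154 for creatinine and −0.203 for age.

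**Formula.** In a ratio of two values from one patient the constant and the sex factor cancel:

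eGFR₂ / eGFR₁ = (Scr₂ / Scr₁)^−1.154 × (age₂ / age₁)^−0.203

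Setting the ratio to 0.80 gives the creatinine rise that triggers the flag:

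Scr₂ / Scr₁ = [(age₂ / age₁)^−0.203 / 0.80]^(1/1.154)

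For age 12 at week 144, the age factor is (14.76 / 12)^−0.203 = 0.959 and the critical ratio is (0.959 / 0.80)^0.867 = 1.170.

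| Age at entry | Week | eGFR change with flat creatinine | Creatinine rise that gives a 20% decline |
|---|---|---|---|
| 12 | 48 | −1.5% | 19.8% |
| 12 | 96 | −2.9% | 18.3% |
| 12 | 144 | −4.1% | 17.0% |
| 16 | 144 | −3.2% | 18.0% |
| 40 | 144 | −1.3% | 19.9% |

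The critical rise at age 12 is only about three points below that at age 40. The problem is therefore less the threshold than its meaning: in a growing patient the rise may come from growth.

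**Below and above the threshold.** For entry at 12 and assessment at week 144:

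| Creatinine rise | 10% | 15% | 20% | 30% | 40% |
|---|---|---|---|---|---|
| MDRD change | −14.1% | −18.4% | −22.3% | −29.2% | −35.0% |

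Rises of 10% and 15% are not flagged, yet they pull down the mean and percentage change.

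**Effect on the overall proportion.** Added false events = 1,300 × share of adolescents × fraction of them crossing through growth. Both factors are assumptions, the fraction being varied from 10% to 80%.

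| Assumed adolescent share | Number in 1,300 | False events | Points added to the overall proportion |
|---|---|---|---|
| 0.5% | 6.5 | 0.7–5.2 | 0.05–0.4 |
| 1% | 13 | 1.3–10.4 | 0.1–0.8 |
| 2% | 26 | 2.6–20.8 | 0.2–1.6 |
| 5% | 65 | 6.5–52 | 0.5–4.0 |

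For scale, the 95% half-width at a true rate of 5% is 1.96 × √(0.05 × 0.95 / 1300) = 1.2 percentage points.

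**Unit wording.** Section 3.1 uses mL/min/1.73 m² for GFR and section 3.2 uses mg/dL for serum creatinine. The unit that 7.2 assigns to creatinine is that of eGFR, so the slip shows from the protocol alone.

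**The case against.** The best defence is that few adolescents will enrol. The feasibility survey in section 6 covered infectious disease physicians in general and infectious disease hospitals, with no paediatric site mentioned, and participants must be able to upload data by smartphone. At a share of 0.5% to 1% the overall proportion moves by less than one point. The study is descriptive and tests no formal hypothesis (9.1.1), and the analysis plan could add a rule for minors. This stands as an argument about size. It does not remove the defect, because the protocol itself writes MDRD into the endpoint without an age limit.

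Four stronger readings are tempting, and the documents do not support them.

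- *That the >20% endpoint in adolescents mostly measures growth.* No creatinine course for adolescents is given. An assumed rise from 0.50 to 0.60 mg/dL between ages 12 and 15 gives (1.20)^−1.154 × (1.25)^−0.203 = 0.774, or −22.6%. Ending at 0.58 instead gives 0.805, or −19.5%, and no flag. Some growing patients will cross and some will not.
- *That the artefact decides the youngest age subgroup.* Age is a subgroup factor in sections 4 and 9.3.2 without cut-points. A youngest stratum reaching into adulthood would dilute the effect.
- *That the error cannot be repaired later.* Age is collected, so adults can be separated at analysis. Only a height-based estimate depends on data not listed for follow-up.
- *That the unit wording will corrupt eGFR.* Creatinine at and after entry goes to a central laboratory, and records from before entry concern a group kept below 10%. A value computed in the wrong unit would be grossly implausible and probably noticed.

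**Conclusion.** The point holds in a limited form. Following the protocol as written, a creatinine rise from growth at constant true GFR is counted as eGFR loss in participants still growing, and a rise of about 17% to 20% in a patient aged 12 at entry counts as a renal safety event. Smaller rises bias the continuous eGFR summaries in the same direction.

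The conclusion rests on two things outside the text: that MDRD has no body-size term, and its standard exponents. The protocol supplies the age limit, the sole equation, the endpoint and the absence of follow-up height. The overall effect is probably small but cannot be fixed without the number of adolescents. It would be concentrated in any young-age stratum and in the age coefficient of the eGFR model. The sample size is unaffected. The change is worth making because it is cheap, not because the main renal result is in danger.

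**What to change.** In 7.2 and 9.3.3, restrict the MDRD-based eGFR endpoints and the eGFR mixed model to participants aged 18 or over at baseline. Splitting by age at baseline means that nobody changes equation on turning 18 during follow-up.

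Report participants under 18 at baseline separately. Where a height close to the creatinine date is available from routine care, use one height-based paediatric equation throughout, at baseline and follow-up alike; otherwise describe serum creatinine. Add an optional follow-up height field for these participants. It should stay optional, because a compulsory measurement would conflict with the non-interventional design in 5.1, section 7 and the notes to the Schedule of Activities.

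Correct the creatinine unit in 7.2 to the one the equation uses.

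The cost is protocol wording and one optional data field. A small group leaves the main eGFR summaries, and some of its heights will be missing.
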